## **8 CONFIDENTIALITY, BIAS, AND MASKING**

### **8.1 Subject Confidentiality and Methods Used to Minimize Bias**

The Investigator must ensure that the subject's anonymity is maintained throughout the course of the study. In particular, the Investigator must keep an enrollment log with confidential identifying information that corresponds to the subject numbers and initials of each study participant. At the end of the clinical study, the Sponsor will collect a copy of the enrollment log without any identifying subject information. All documents submitted to the Sponsor will identify the subjects exclusively by number and demographic information. No other personally identifying information should be transmitted to the Sponsor.

This study is subject-masked with subjects randomized to use LID017569 or Biofinity for 30 days and then crossover and use the other study product for 30 days. The Sponsor personnel (other than site monitors, lead clinical site manager, CDMA PL, Alcon Observer, person responsible for generating the randomization schedule, and unmasked clinical data managers) involved in reporting, obtaining, and/or reviewing the clinical evaluations will be masked to the identity of the contact lens being administered. This level of masking will be maintained throughout the conduct of the study. Unmasking will occur only after all planned study data have been validated, and the database locked.

Masked study personnel must avoid seeking information that may compromise masking. Unmasked study personnel must not disseminate information that is potentially unmasking to

any masked personnel. The **masked** and **unmasked** site personnel must coordinate all study activities as necessary to protect masking and minimize bias during the trial.

## 8.2 Unmasking of the Study Treatment

Investigators are unmasked in this study. However, the identity of the assigned medical device should not be disclosed to subjects who are masked during the study. The Study Sponsor must be informed of all cases in which unmasking of the subject(s) has occurred and of the circumstances involved. The Study Sponsor should be informed in advance of unmasking when possible, except in the event of a medical emergency. Additionally, the Study Sponsor may be required to unmask the information in order to fulfill expedited regulatory reporting requirements.

## 9 DATA HANDLING AND ADMINISTRATIVE REQUIREMENTS

### 9.1 Completion of Source Documents and Case Report Forms

The nature and location of all source documents will be identified to ensure that original data required to complete the eCRFs exist and are accessible for verification by the site monitor, and all discrepancies shall be appropriately documented via the query resolution process. Study monitors are appointed by the Study Sponsor and are independent of study site staff. If electronic records are maintained, the method of verification must be determined in advance of starting the study.

At a minimum, source documents should include the following information for each subject:

- Subject identification (name, sex, race/ethnicity)
- Documentation of subject eligibility
- Date of informed consent
- Dates of visits
- Documentation that protocol specific procedures were performed
- Results of study parameters, as required by the protocol
- IP accountability records
- Documentation of AEs and other safety parameters (if applicable)
- Records regarding medical histories and the use of concomitant therapies prior to and during the study

- Date of study completion and reason for early discontinuation, if applicable

It is required that the author of an entry in the source documents be identifiable. Direct access to source documentation (medical records) must be allowed for the purpose of verifying that the data recorded on the eCRF are consistent with the original source data.

Only designated individuals may complete the eCRFs. The eCRFs will be submitted at regular intervals following the clinical study visit schedule. It is expected that all data reported will have corresponding entries in the source documents. The Principal Investigator is responsible for reviewing and certifying that the eCRFs are accurate and complete. The only subject identifiers recorded on the eCRFs will be subject number, and subject demographic information.

## **9.2 Data Review and Clarifications**

Upon completion of the eCRFs, a targeted review of the eCRF data to the subject's source data will be completed by the site monitor to ensure completeness and accuracy. Additional data clarifications and/or additions may be needed as a result of the data cleaning process. Data clarifications are documented and are part of each subject's eCRFs.

## **9.3 Regulatory Documentation and Records Retention**

The Investigator is required to maintain up-to-date, complete regulatory documentation as indicated by the Sponsor and the Investigator's files will be reviewed as part of the ongoing study monitoring. Financial disclosure is not subject to regulatory inspection and should be kept separately.

Additionally, the Investigator must keep study records and source documents until the Sponsor provides written approval for their destruction. If the Investigator retires, relocates, or for any other reason withdraws from responsibility of keeping the study records, the Sponsor must be notified and suitable arrangements made for retention of study records and source documents needed to comply with national and international regulations (generally 2 years after discontinuing clinical development or after the last marketing approval).

## **10 ETHICS AND COMPLIANCE**

This trial will be conducted in accordance with the ethical principles that have their origin in the Declaration of Helsinki and the referenced directives, regulations, guidelines, and/or standards.

## 10.1 Compliance

The Investigator must ensure that all personnel involved in the conduct of the study are qualified to perform their assigned responsibilities through relevant education, training, and experience. The Investigator and all clinical study staff must conduct the clinical study in compliance with the protocol. Deviations from this protocol, regulatory requirements and/or GCP must be recorded and reported to the Sponsor prior to database lock. If needed, corrective and preventive action should be identified, implemented, and documented within the study records.

## 10.2 Institutional Review Board (IRB)

This trial requires IRB approval prior to initiation. This protocol, subject informed consent, and subsequent amendments will be reviewed and approved by an IRB.

Before clinical study initiation, this protocol, the ICF (and assent form, if applicable), any other written information given to subjects, and any advertisements planned for subject recruitment must be approved by an IRB. The Investigator must provide documentation of the IRB approval to the Study Sponsor. The approval must be dated and must identify the applicable protocol, amendments (if any), ICF, assent form (if any), all applicable recruiting materials, written information for subject, and subject compensation programs. The IRB must be provided with a copy of the Investigator's Brochure and Package Insert, any periodic safety updates, and all other information as required by local regulation and/or the IRB. At the end of the study, the Investigator must notify the IRB about the study's completion. The IRB also must be notified if the study is terminated prematurely. Finally, the Investigator must report to the IRB on the progress of the study at intervals stipulated by the IRB.

Voluntary informed consent must be obtained from every subject prior to the initiation of any screening or other study-related procedures. The Investigator must have a defined process for obtaining consent. Specifically, the Investigator, or delegate, must explain the clinical study to each potential subject and the subject must indicate voluntary consent by signing and dating the approved informed consent form. The subject must be provided an opportunity to ask questions of the Investigator, and if required by local regulation, other qualified personnel. The Investigator must provide the subject with a copy of the consent form written in a language the subject understands. The consent document must meet all applicable local laws and provide subjects with information regarding the purpose, procedures, requirements, and restrictions of the study, along with any known risks and potential benefits associated with the IP, the available compensation, and the established provisions for maintaining confidentiality of personal, protected health information. Subjects will be told about the voluntary nature of participation in the study and must be provided with contact information

for the appropriate individuals should questions or concerns arise during the study. The subject also must be told that their records may be accessed by appropriate authorities and Sponsor-designated personnel. The Investigator must keep the original, signed copy of the consent and must provide a duplicate copy to each subject according to local regulations. Following this study, the subject will return to their eye care professional for their routine eye care and contact lenses.

### 11 PROTOCOL AMENDMENT HISTORY

Version	Brief Description and Rationale
1	Initial Version of this document
2	Revisions to the protocol include: 
 
Updated Sponsor Name on title page to reflect 'Alcon Research, LLC and its affiliates ("Alcon")'
 
[REDACTED]
 
[REDACTED]
 

**Job Notes:**

This is the first revision (Version 2.0) of the Statistical Analysis Plan for this study. This version of the Statistical Analysis Plan is based on Version 2.0 of the study protocol.

## **Executive Summary:**

### Key Objective:

The primary objective of this study is to describe the clinical performance of an investigational silicone hydrogel contact lens over 30 days of daily wear.

### Decision Criteria for Study Success:

Decision criteria for study success are not applicable for this study.

**List of Figures**

**No table of figures entries found.**

# 1 Study Objectives and Design

## 1.1 Study Objectives

### PRIMARY OBJECTIVE

The primary objective of this study is to describe the clinical performance of an investigational silicone hydrogel contact lens over 30 days of daily wear.

## 1.2 Study Description

Key components of the study are summarized in Table 1-1.

**Table 1-1 Study Description Summary**

Study Design	Prospective, randomized, single-masked, bilateral crossover
Study Population	Volunteer subjects aged 18 or over who are habitual spherical weekly/monthly soft contact lens wearers (excluding Biofinity wearers), have at least 3 months of contact lens wearing experience, and who wear their habitual lenses at least 5 days per week and at least 8 hours per day.  Target to complete: 32; Planned to enroll: ~36
Number of Sites	~3 US
Test Product	LID017569
Control Product	CooperVision® Biofinity® contact lenses (Biofinity)
Duration of Treatment	~ 60 days total duration (test and control) Test Product: ~30 days Control Product: ~30 days
Visits	Visit 1 – Screen/Baseline/ Lens 1: Dispense [Day 1] Visit 2 – Lens 1: Week 1 Follow-up [Day 8 ±2 Days] Visit 3 – Lens 1: Month 1 Follow-up [Day 30 ± 2 days]/Lens 2 – Dispense [Day 1] Visit 4 – Lens 2: Week 1 Follow-up [Day 8 ± 2 days] Visit 5 – Lens 2: Month 1 Follow-up/Exit [Day 30 ± 2 days]

### **1.3 Randomization**

A member of the Randomization Programming group at Alcon who is not part of the study team will generate the randomized allocation schedule(s) for study lens sequence assignment.

### **1.4 Masking**

This is a single-masked (trial subject) study.

### **1.5 Interim Analysis**

There are no plans to conduct an interim analysis and no criteria by which the study would be terminated early based upon statistical determination.

## **2 Analysis Sets**

### **2.1 Safety Analysis Set**

Safety analyses will be conducted using the safety analysis set on a treatment-emergent basis. As such, the safety analysis set will include all subjects/eyes exposed to any study lenses evaluated in this study. For treatment-emergent safety analyses, subjects/eyes will be categorized under the actual study lenses exposed in the corresponding lens sequence.

Adverse events occurring from the time of informed consent but prior to first exposure to study lenses will be summarized in subject listings.

## **3 Subject Characteristics and Study Conduct Summaries**

The following tables will be presented:

- Subject Disposition by Lens Sequence
- Analysis Set by Lens Sequence
- Analysis Set by Lens
- Subject Accounting by Lens Sequence
- Demographics Characteristics by Lens Sequence
- Baseline Characteristics by Lens Sequence

In addition, the following subject listings will be provided:

- Listing of Subjects Excluded from Protocol Defined Analysis Set
- Listing of Lens Sequence Assignment by Investigator
- Listing of Subjects Discontinued from Study

## 4 Effectiveness Analysis Strategy

This study defines one primary endpoint [REDACTED]. The safety analysis set will be used for all effectiveness analyses.

Continuous variables will be summarized using the number of observations, mean, standard deviation, median, minimum, and maximum. Categorical variables will be summarized with counts and percentages from each category.

All data obtained in evaluable subjects/eyes will be included in the analysis. No imputation for missing values will be carried out.

A listing of selected effectiveness data will also be provided.

### 4.1 Effectiveness Endpoints

#### Primary Endpoint

The primary endpoint is distance visual acuity (VA) with study lenses, collected in logMAR, for each eye.

[REDACTED]

[REDACTED]

[REDACTED]

- [REDACTED]
- [REDACTED]
- [REDACTED]
- [REDACTED]
- [REDACTED]
- [REDACTED]
- [REDACTED]
- [REDACTED]
- [REDACTED]
- [REDACTED]
- [REDACTED]

[Redacted]

## 4.2 Effectiveness Hypotheses

### Primary Effectiveness

No inferences are to be made on the primary effectiveness endpoint; therefore, no hypotheses are formulated.

[Redacted]

## 4.3 Statistical Methods for Effectiveness Analyses

### 4.3.1 Primary Effectiveness Analyses

Descriptive statistics (number of observations, mean, standard deviation, median, minimum, maximum) for the logMAR values will be presented.

[Redacted]

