**Table 1-1 Schedule of Study Procedures and Assessments**

Procedure/ Assessment	Visit 1 Screen / Baseline/ Lens 1: Dispense [Day 1]	Visit 2 Lens 1: Week 1 Follow-up [Day 8 (± 2 days)] §	Visit 3 Lens 1: Month 1 Follow-up [Day 30 (± 2 days)] Lens 2: Dispense [Day 1]		Visit 4 Lens 2: Week 1 Follow-up [Day 8 (± 2 days)] §	Visit 5 Lens 2: Month 1 Follow-up/ Exit^ [Day 30 (± 2 days)] §	Unscheduled Visit
			Follow-up Lens 1 §	Dispense Lens 2			
Informed Consent	X						
Demographics	X						
Medical History	X	X	X	X	X	X	X
Concomitant Medications	X	X	X	X	X	X	X
Inclusion/ Exclusion	X						
Habitual lens (brand, power*, care)	X						
VA w/ habitual correction* (OD, OS, logMAR distance)	X					X	(X)
████████████████████	█		█			█	
Manifest refraction*	X	(X)	(X)	(X)	(X)	(X)	(X)
BCVA* (OD, OS, logMAR distance with manifest refraction)	X	(X)	(X)	(X)	(X)	(X)	(X)
Biomicroscopy	X	X	X		X	X	X
████████████████████	█	█	█	█	█	█	█
Randomization	X						
Dispense study lenses	X			X			(X)
VA w/ study lenses, (OD, OS, logMAR distance)	X	X	X	X	X	X	(X)
████████████████████	█	█	█	█	█	█	█
████████████████████	█	█	█	█	█	█	█

Printed By:

Print Date:

Procedure/ Assessment	Visit 1 Screen / Baseline/ Lens 1: Dispense [Day 1]	Visit 2 Lens 1: Week 1 Follow-up [Day 8 (± 2 days)] §	Visit 3 Lens 1: Month 1 Follow-up [Day 30 (± 2 days)] Lens 2: Dispense [Day 1]		Visit 4 Lens 2: Week 1 Follow-up [Day 8 (± 2 days)] §	Visit 5 Lens 2: Month 1 Follow-up/ Exit^ [Day 30 (± 2 days)] §	Unscheduled Visit
			Follow-up Lens 1 §	Dispense Lens 2			
[REDACTED]	[REDACTED]	[REDACTED]	[REDACTED]	[REDACTED]	[REDACTED]	[REDACTED]	[REDACTED]
[REDACTED]	[REDACTED]	[REDACTED]	[REDACTED]	[REDACTED]	[REDACTED]	[REDACTED]	[REDACTED]
[REDACTED]	[REDACTED]	[REDACTED]	[REDACTED]	[REDACTED]	[REDACTED]	[REDACTED]	[REDACTED]
[REDACTED]	[REDACTED]	[REDACTED]	[REDACTED]	[REDACTED]	[REDACTED]	[REDACTED]	[REDACTED]
[REDACTED]	[REDACTED]	[REDACTED]	[REDACTED]	[REDACTED]	[REDACTED]	[REDACTED]	[REDACTED]
[REDACTED]	[REDACTED]	[REDACTED]	[REDACTED]	[REDACTED]	[REDACTED]	[REDACTED]	[REDACTED]
[REDACTED]	[REDACTED]	[REDACTED]	[REDACTED]	[REDACTED]	[REDACTED]	[REDACTED]	[REDACTED]
[REDACTED]	[REDACTED]	[REDACTED]	[REDACTED]	[REDACTED]	[REDACTED]	[REDACTED]	[REDACTED]
AEs	X	X	X	X	X	X	X
Device deficiencies	X	X	X	X	X	X	X
Exit Form	(X)	(X)	(X)	(X)	(X)	X	(X)

\* Source only

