### 3.5 Outline of Study

This will be a multi-site, prospective, randomized, subject-masked study comparing 2 contact lenses. The duration of subject participation in the study is up to 64 days, with 5 scheduled visits. The study is expected to be completed in approximately 3 months.

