## 4 TREATMENTS ADMINISTERED

Subjects will be randomized in a 1:1 manner to receive treatment in crossover sequence: Test product then Control product or Control product then Test product, respectively.

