### 6.4.1.2 Analysis Methods

Descriptive statistics will be presented.

[Redacted]

- | [Redacted]
- | [Redacted]
- | [Redacted]
- | [Redacted]
- | [Redacted]
- | [Redacted]
- | [Redacted]
- | [Redacted]
- | [Redacted]
- | [Redacted]
- | [Redacted]
- | [Redacted]
- | [Redacted]

[Redacted]

[Redacted]

[Redacted]

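### Does the primary analysis need a within-subject lens difference because the trial is a crossover?

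*SAP*

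**What the plan says.** SAP 4.3.1 gives the primary analysis in one visible sentence: "Descriptive statistics (number of observations, mean, standard deviation, median, minimum, maximum) for the logMAR values will be presented". Protocol 6.4.1.2 is shorter: "Descriptive statistics will be presented". In both documents blacked-out text follows directly. SAP 4.1 defines the endpoint: "The primary endpoint is distance visual acuity (VA) with study lenses, collected in logMAR, for each eye". SAP 4 adds: "A listing of selected effectiveness data will also be provided".

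The design is set out in SAP Table 1-1 ("Prospective, randomized, single-masked, bilateral crossover") and Protocol 4 ("Subjects will be randomized in a 1:1 manner to receive treatment in crossover sequence"). Protocol 3.5 introduces it in these terms: "This will be a multi-site, prospective, randomized, subject-masked study comparing 2 contact lenses". Protocol Table 1-1 schedules acuity with the study lenses at dispensing, Week 1 and Month 1 of each period.

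The objective, identical in Protocol 3.2 and SAP 1.1, is descriptive and names only the investigational lens. The SAP Executive Summary states that success criteria do not apply. Protocol 6.4.1.1 and SAP 4.2 rule out inference on the primary endpoint, and Protocol 6.7 and SAP 4.4 confirm that nothing is formally tested.

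**The concern.** The usual reason to run a crossover is that each subject serves as their own control. A statistician who sees two randomised sequences, both lenses worn by each completer and repeated acuity measurements under each lens expects a summary of the difference within subject. The visible plan lists only statistics of the acuity values themselves.

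Those statistics cannot replace the missing one. Among subjects with both periods, the difference between the two lens means equals the mean paired difference. The spread of the differences, however, depends on the within-subject correlation, which summaries of each lens do not carry. Anyone wanting the precision of test minus control would have to treat the columns as independent or guess a correlation. If the study were meant to estimate that contrast, this would discard information already collected.

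**Working it through.** **1. The plan's own figures.** The plan gives no figure on this point. The visible sample-size figures are about 36 enrolled and 32 completing (Protocol 3.4). They agree with each other: 3 sites × 12 = 36, and (36 − 32)/36 = 11.1% allowed for screen failure and early exit. The visible text gives no SD, correlation, margin, alpha or power, so the 32 cannot be derived from it.

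**2. What pairing would change.** The inputs are n = 32 (documents), an SD of 0.08 logMAR at subject level for each lens (assumed), a within-subject correlation ρ (assumed) and no period effect.

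- SD of the difference = SD × √(2(1 − ρ)).
- Paired 95% half-width = t(0.975, 31) × SD × √(2(1 − ρ)/32), with t = 2.040.
- Half-width with the columns taken as independent = t(0.975, 62) × SD × √(2/32) = 1.999 × 0.08 × 0.25 = 0.040.

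| ρ | SD of difference | Paired half-width | Paired / independent |
|---|---|---|---|
| 0.1 | 0.107 | 0.039 | 0.97 |
| 0.2 | 0.101 | 0.036 | 0.91 |
| 0.3 | 0.095 | 0.034 | 0.85 |
| 0.5 | 0.080 | 0.029 | 0.72 |
| 0.7 | 0.062 | 0.022 | 0.56 |
| 0.9 | 0.036 | 0.013 | 0.32 |

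For ρ = 0.3 / 0.5 / 0.7 / 0.9, an SD of 0.06 gives 0.026 / 0.022 / 0.017 / 0.010 against 0.030, and an SD of 0.10 gives 0.043 / 0.036 / 0.028 / 0.016 against 0.050. The ratio does not depend on the SD. The gain vanishes at ρ = 1 − (1.999/2.040)² ≈ 0.04. The documents cannot place ρ. The entry limit on best corrected acuity and the acuity required before a subject leaves with the lenses (Protocol 5.1.1 and 5.1.3) may narrow between-subject spread and push ρ down, where the gain is small.

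**3. Whether the plan uses that quantity.** Set against the sections above:

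- Objective: one lens, described. Location, spread and range of acuity answer it.
- Inference: excluded, so no interval or test on the lens contrast is planned in the visible text. The half-widths above, paired or not, appear nowhere in it.
- Decision: none is attached to the result, so a narrower or wider contrast alters no conclusion.
- Comparison: the outline sentence in Protocol 3.5 describes the design. It sets no objective and defines no estimand.

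**4. Unit of analysis.** The endpoint is per eye, whereas the calculation in step 2 is per subject. Its half-widths are therefore not a reading of the planned table. If the observations counted are eyes, the printed n and SD should not be turned into a standard error without allowing for the correlation between eyes. This too matters only for an inference the plan does not make.

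**5. What the documents can show.** The text after SAP 4.3.1 and after Protocol 6.4.1.2 is blacked out, and so is the content of SAP 7. The SAP table of contents has an entry with its title removed after 4.3.1, so part of the hidden text may be a separate subsection. Absence from the visible text is not absence from the plan.

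**The case for a change.** The best case for the concern is that the spread of individual differences is itself description. Take SD 0.08, equal means and normal data, all assumed. The same per-lens tables then fit about 29%, 21% or 0.5% of subjects differing by at least 0.10 logMAR between lenses, at ρ = 0.3, 0.5 or 0.9. Protocol 3.1 says the data are to inform product development, and a developer might want to know which of these applies. There is no imputation, and the analysis set takes in anyone exposed to either lens, so the two lens summaries may also rest on slightly different subjects. The listing in SAP 4 is not visibly said to contain acuity or to pair the lenses. One more table would need no new data and no alpha.

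The algebra stands, and so does the point that such a table would fit a descriptive study. The step from useful to required does not. The question of how far each subject's two lenses differ is one the visible plan never sets, and answering it would not change how the investigational lens is described. The proposal would also bring in choices the visible plan does not contain: averaging eyes for a per-eye endpoint, a subset of subjects with both periods, and a split by sequence with about 16 subjects in each.

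**Conclusion.** The concern does not hold. Followed as written, the visible primary analysis gives a sound answer to the question the trial sets, and no stated figure is wrong. The possible gain in precision runs from 3% narrower at ρ = 0.1 to 68% narrower at ρ = 0.9. It rests wholly on assumed SDs and correlations and applies to a test-minus-control interval that the plan disclaims. Its effect on planned results and decisions is nil. A within-subject table would be a reasonable extra if the sponsor wants it, and the redactions leave open that one is already planned. This judgement rests on the stated objective and the absence of inference. It would change if the study were used to support a comparative claim about the two lenses.
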